### 5.1.3 Secondary Outcomes

The evaluation of secondary outcomes is performed in an explorative manner without adjustment for multiplicity and evaluated in the ITT population.

### At NH level:

All secondary endpoints are count data.

For the endpoints 1,2, 4 and 5 c. & d., a Poisson Regression model is calculated with the respective number per 100 residents per past 12 months' observation period (from t1 to t2) as dependent variable, group (intervention vs control) as independent variable, number of occupied bed days as offset and the respective baseline rate and region of NHs as covariates.

The treatment effect is presented as incidence rate ratio (IRR) with corresponding 95%-CI and p-value. Marginal estimators (numbers per 100 residents per past 12 -months observation period (from t1 to t2)) with corresponding 95%-CI are given per treatment group.

For the secondary endpoint 3, the number of residents during the observation period before t2 is used as offset variable. The resulting marginal estimators are numbers per 100 residents.

The secondary endpoints 5 a. & b. and 6-7, 8 a. and 9 a. are measured cross-sectional. For these endpoints, a Poisson Regression model is calculated with the respective number as dependent variable, group (intervention vs. control) as independent variable, number of residents as offset and the respective baseline rate and region of NHs as covariates.

The treatment effect is presented as IRR with corresponding 95%-CI and p-value. Marginal estimators (numbers per 100 residents per past 12 -months observation period (from t1 to t2)) with corresponding 95%-CI are given per treatment group.

The secondary endpoints 8 b. - d. and 9 b. - e. are measured cross-sectional, too, but refer to a predefined subgroup.

For these endpoints, a Poisson Regression model is calculated with the respective number as dependent variable, group (intervention vs control) as independent variable and the respective baseline rate and region of NHs as covariates.

For the endpoints 8 b. - d. the number of ADs and for the endpoints 9 b. - e. the number of POLST-Es are set as offset, respectively.

The treatment effect is presented as IRR with corresponding 95%-CI and p-value. Marginal estimators (number per 100 ADs or 100 POLST-Es per past 12 -months observation period (from t1 to t2)) with corresponding 95%-CI are given per treatment group.

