## 2 Study Methods

## 2.1 Trial design

BEVOR is a two-arm, parallel group, prospective, multicenter, cluster randomized controlled trial (cRCT). Nursing homes and related health care providers form the clusters and they themselves (DC1) or, respectively, their residents (DC2) the observation units. The allocation ratio of the clusters is 1:1 for the two groups:

- ACP program (experimental treatment group):
   Each nursing home and related care providers will receive an institutional and regional implementation of the complex German ACP program including a ACP facilitator .
- Care as usual (control group): For each nursing home and health care provider all common care options within the German health care system are available. The control group will receive a delayed ACP intervention after final data collection.

The trial is observer blinded (outcome assessors (until finalization of the SAP) and data collectors are blinded).

44 nursing homes with an average of 96 residents each, from the 4 study centres in Düsseldorf (2 regions), Munich (2 regions), Halle (2 regions) and Göttingen (2 regions) are participating.

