### 2.3 Sample size

To be allocated to trial: 44 NHs (22 per group) including on average n = 100 residents each, resulting in a target sample size of n = 4.400 (2.200 per group) enrolled patients in total.

To be analysed: n = 1760 residents in 22 NHs per group and n = 3520 residents in 44 NHs in total. Full details of sample size calculation can be found in the study protocol [2].

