## 3 Statistical Principles

### 3.1 Confidence intervals and P values

All applicable statistical tests will be two-sided and at a 5% significance level. Analyses of secondary outcomes will be performed without adjustment for multiplicity. All confidence intervals presented will be 95% and two-sided.

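### The Poisson models for the home-level secondary endpoints 3, 5a-b and 6 to 9 name no variance correction, so their intervals can be too narrow or too wide, depending jointly on prevalence and between-home variation

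*SAP*

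**What the plan says.** SAP section 5.1.3, under the home-level heading, opens with "All secondary endpoints are count data". It then assigns a Poisson regression to each endpoint.

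- Endpoint 3 (residents hospitalised at least once): the offset is the number of residents in the observation period.
- Endpoints 5a-b, 6, 7, 8a and 9a: the model has "group (intervention vs. control) as independent variable, number of residents as offset and the respective baseline rate and region of NHs as covariates".
- Endpoints 8b-d and 9b-e: "For the endpoints 8 b. - d. the number of ADs" serves as offset, and for 9b-e the number of POLST-Es.

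Each result is to be an IRR with a 95% CI and p-value. Section 3.1 sets the standard: "All applicable statistical tests will be two-sided and at a 5% significance level". No dispersion parameter, home random effect or robust variance is named for these models.

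Section 5.2 plans a negative binomial analysis for the primary endpoint only. The key secondary endpoints (9e, 10a ii and 10b ii, section 1.2.2) receive per-protocol, adherence and adjusted analyses.

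The resident-level counterparts of several of these quantities (20, 22, 29 and items of 31) are treated in the same section as binary, with mixed logistic models and a home random intercept.

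**The concern.** Endpoints 3, 5a-b, 8b-d and 9b-d are k out of n: the numerator is a subset of the denominator. Endpoints 6, 7, 8a and 9a count guardians or documents. They have the same ceiling only if each resident contributes at most one, which the SAP does not state.

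A plain Poisson variance is wrong for such data in two opposing ways. It ignores the ceiling, which overstates within-home variance. It also ignores differences between homes in underlying prevalence, which understates total variance. The two errors cancel only by coincidence.

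At stake are the CIs and p-values of these endpoints: false positives where between-home variation dominates, and missed effects where the ceiling dominates. Key endpoint 9e is among them, and its per-protocol, adherence, adjusted and subgroup analyses build on the same model.

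**Working it through.** **Inputs from the SAP.** Section 2.1 gives "44 nursing homes with an average of 96 residents each" in 8 regions (4 centres, 2 each), randomised 1:1. Section 3.1 gives two-sided 5%. The SAP states no prevalence, ICC or standard error for these endpoints, so there is no figure of its own to reproduce.

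**Assumptions.** Prevalence p, between-home ICC (or SD) and a t0-t2 home correlation of 0.5 are assumed and varied.

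**Step 1: variance ratio.** With m residents per home, the true variance of k is m·p(1-p)·[1+(m-1)ICC]. The Poisson variance is m·p. Hence

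ratio = (1-p)·[1+(m-1)ICC], and coverage of a nominal 95% interval = 2Φ(1.96/√ratio) - 1.

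With m = 96, for example p = 0.5 and ICC = 0.05: 0.5 × (1 + 95 × 0.05) = 0.5 × 5.75 = 2.88, so coverage is 75%.

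| p | ICC 0: ratio, coverage | ICC 0.02 | ICC 0.05 |
|---|---|---|---|
| 0.05 | 0.95, 95.6% | 2.76, 76% | 5.46, 60% |
| 0.3 | 0.70, 98% | 2.03, 83% | 4.02, 67% |
| 0.5 | 0.50, 99.4% | 1.45, 90% | 2.88, 75% |
| 0.7 | 0.30, ~100% | 0.87, 96% | 1.73, 86% |
| 0.9 | 0.10, ~100% | 0.29, ~100% | 0.57, 99% |

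AD and POLST-E denominators may be smaller than 96. With m = 50 and ICC 0.05, the ratio is 2.42 (79%) at p = 0.3 and 0.34 (99.9%) at p = 0.9, so the pattern is the same.

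**Step 2: break-even.** The ratio equals 1 when ICC = p/[(1-p)(m-1)]. With m = 96 this is 0.0006 at p = 0.05, 0.0045 at 0.3, 0.0105 at 0.5, 0.025 at 0.7 and 0.095 at 0.9. Seen the other way, at ICC 0.02 the ratio is 2.9(1-p), which exceeds 1 up to about p = 0.65.

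**Step 3: simulation of the planned model.** 44 homes of about 96 residents in 8 regions, no treatment effect, beta-binomial counts, 1,500 runs per cell. The model was Poisson with group, baseline rate and region as covariates, a log offset and default standard errors. Type I error at p = 0.05, 0.3, 0.6 and 0.9 was:

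- ICC 0: 4.3%, 1.5%, 0.3%, 0.0%
- ICC 0.05: 35.5%, 29.3%, 17.1%, 0.6%

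Over all 16 cells (ICC up to 0.15) the range was 0.0% to 58.5%.

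**Step 4: the same in between-home SD.** ICC = SD²/[p(1-p)]. At a t0-t2 correlation of 0.5, baseline adjustment leaves at best 1 - 0.5² = 0.75 of it. Expected type I error is 2[1 - Φ(1.96/√ratio)].

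| p, SD | ICC | × 0.75 | ratio | expected | simulated |
|---|---|---|---|---|---|
| 0.8, 5 points | 0.016 | 0.012 | 0.42 | 0.3% | 0% |
| 0.8, 15 points | 0.141 | 0.105 | 2.20 | 19% | 20% |
| 0.5, 5 points | 0.010 | 0.0075 | 0.86 | 3% | 4% |
| 0.5, 15 points | 0.090 | 0.068 | 3.71 | 31% | 32% |
| 0.3, 15 points | 0.107 | 0.080 | 6.04 | 43% | 43% |

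Formula and simulation agree. At p = 0.8 the error reverses direction when only the SD changes.

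**Step 5: the correction.** Keeping the Poisson model and scaling its standard error by the square root of Pearson χ²/df, with a t reference, gives 3.5% to 5.7% in the Step 4 settings. In Step 3 it gives 4.0% to 6.4% in 15 of 16 cells, and 9.5% in the sparse cell (p = 0.05, ICC 0.15).

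**The case against.** **The SAP never says model-based standard errors.** This is true: the default is inferred from silence. A log-link Poisson model with robust standard errors is a valid ratio analysis of k-of-n data, so Poisson regression is not itself the error. What stands is that the variance is left unstated, and the default is what results if the text is followed as written.

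**Prevalence alone might seem to set the direction.** A reader could infer that common items get wide intervals and rare ones narrow intervals. Step 4 does not support this: at p = 0.8 the interval is too wide with an SD of 5 points and too narrow with 15. At p = 0.5 with an SD of 5 points it is close to correct.

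**Key endpoint 9e might be read as a POLST-E prevalence with a known error.** The document does not support that. Section 1.2.2 defines 9e per 100 residents, but section 5.1.3 gives it the number of POLST-Es as offset. Under the offset it is a share of POLST-Es; under the definition it is a rate among residents. The direction of its error cannot be stated until the two are reconciled.

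**All these endpoints might be called proportions, with fitted values above 100 per 100.** The ceiling for 6, 7, 8a and 9a is conditional, as noted above, and no such fitted value has been shown.

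**The analyses are exploratory, and some quantities are also analysed at resident level.** Both are true, and they limit the impact. But section 5.1.3 waives multiplicity adjustment, not valid intervals, and the resident-level models cover only consenting long-term residents. Section 5.4.3 allows sensitivity models for secondary endpoints if of interest, but outside the study report.

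**Conclusion.** The concern holds in this form: the plan names no variance that allows for the ceiling or for between-home variation in the home-level endpoints 3, 5a-b, 6-7, 8a-d and 9a-e, and no planned check fills the gap. If the models are run with default standard errors, the reported 95% CIs and p-values are correct only where the ICC happens to sit near its break-even value.

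For the bounded endpoints, type I error ranges from about 0% to about 43% under m = 96, between-home SD of 5 to 15 points and a t0-t2 correlation of 0.5. Prevalence, SD and correlation are all assumed. It is therefore not established that any particular endpoint will be badly off, nor in which direction. For 6, 7, 8a and 9a the formula applies only if each resident contributes at most one; otherwise the unmodelled between-home variation remains a problem.

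This should be corrected, but it does not touch the primary analysis.

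**What to change.** Add one sentence to the home-level part of section 5.1.3: for endpoints 3, 5a-b, 6-7, 8a-d and 9a-e, standard errors are Pearson-scaled (quasi-Poisson) with a t reference on the residual degrees of freedom, or small-sample robust. With 44 homes and 10 mean parameters (group, baseline rate, 8 region levels) that leaves 34 degrees of freedom. The log link, covariates and IRR stay as planned.

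For the endpoints that are truly k of n, quasi-binomial or beta-binomial regression is an acceptable alternative if an OR is acceptable; the change of effect measure is not needed to repair the intervals. Extending the negative binomial check would not be enough, because that model cannot represent variance below the Poisson level. For rare items, read the scaled result with caution, given the 9.5% in the sparse simulated cell.

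Also reconcile the definition of 9e in section 1.2.2 with its offset in section 5.1.3, and say whether 6, 7, 8a and 9a count residents or documents.

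The cost is SAP wording only: no new data and no change of effect measure under the first option.

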### 1.2.2 Secondary Outcomes

The secondary outcomes are as follows, analyzed at t2:

At NH level (DC1):

- 1. number of hospital days (long-term) per 100 residents per past 12 months
- 2. number of hospital stays (long-term) per 100 residents during observation period (without consideration of occupied bed days)
- 3. number of patients with at least one hospitalization per 100 residents per past 12 months
- 4. number of residents who died in the hospital per 100 residents per past 12 months
- 5. number of pre-specified unwanted invasive treatments per 100 residents measured:
  - a. number of residents with feeding tube (PEG) in place (cross-sectional)
  - b. number of residents with PEG in use (cross-sectional)
  - c. number of attempts of cardiopulmonary resuscitation (CPR) per past 12 months
  - d. number of attempts of successful CPR per past 12 months
- 6. number of legal guardians per 100 residents (cross-sectional)
- 7. number of durable powers of attorney (DPOA) per 100 residents (cross-sectional)
- 8. advance directives (ADs)
  - a. number of all advance directives per 100 residents (cross-sectional)
  - b. number of advance directives signed by resident per 100 ADs (cross-sectional)
  - c. number of advance directives last signed in the last 6m per 100 ADs (cross-sectional)
  - d. number of advance directives in long-term care only per 100 ADs (cross-sectional)

- 9. physician or patient/proxy orders for life sustaining treatment in emergencies (POLST-E)
  - a. number of POLST-E per 100 residents (cross-sectional)
  - b. number of POLST-E not signed by resident per 100 POLST-E (cross-sectional)
  - c. number of POLST-E in the last 6m per 100 POLST-E (cross-sectional)
  - d. number of POLST-E with a do-not-hospitalize order per 100 POLST-E (cross-sectional)
  - e. number of POLST-E per 100 residents (long-term care only; cross-sectional)

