### 5.2 Sensitivity analyses

For the primary endpoint analysis, an evaluation with the negative binomial distribution to detect a possible but not expected overdispersion will be performed.

Further, for both primary and key secondary endpoints, per protocol analyses as well as adherence analyses based on NH and resident level will be performed.

Finally, an adjusted analysis is performed taking into account remarkable (p < 0.05) differences at baseline and t1, regarding the following potential confounders:

20

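### Nursing-home-level hospital days (exploratory endpoint 1) are analysed by plain Poisson regression although days come in multi-day stays, so the reported interval is too narrow and the p-value too small

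*SAP*

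**What the plan says.** SAP section 1.2.2 lists as endpoint 1 the "number of hospital days (long-term) per 100 residents per past 12 months", collected as one aggregate per home. Section 5.1.3, under the nursing-home level, gives its model: "For the endpoints 1,2, 4 and 5 c. & d., a Poisson Regression model is calculated", with "number of occupied bed days as offset and the respective baseline rate and region of NHs as covariates". The result is an incidence rate ratio with 95% CI and p-value. Hospital days are thus treated in the same way as counts of stays, in-hospital deaths and resuscitation attempts.

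Section 3.1 sets the error rates: "All applicable statistical tests will be two-sided and at a 5% significance level" and "All confidence intervals presented will be 95% and two-sided".

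On overdispersion, section 5.2 says: "For the primary endpoint analysis, an evaluation with the negative binomial distribution to detect a possible but not expected overdispersion will be performed". Section 5.4.3 permits, but does not require, the sensitivity analyses for secondary endpoints, and keeps them out of the study report. Section 5.1.3 calls the secondary outcomes exploratory. Section 1.2.2 names 9e, 10a ii and 10b ii as the key secondary endpoints, so endpoint 1 is not one of them.

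**The concern.** A Poisson model counts every hospital day as a separate independent event. A resident admitted for eight days contributes eight days at once, and those eight carry the sampling information of one admission. The model-based standard error is therefore too small by construction, before any question of whether homes differ from one another. Region and baseline rate as covariates cannot remove dependence within a stay.

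Hospital use is the trial's central theme, so a reader will set the result for hospital days beside the primary result on hospitalizations. A spuriously significant change, in either direction, could be taken as support for or contradiction of the primary finding.

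**Working it through.** **The plan's own figures.** The SAP states no length of stay, hospital-day rate, dispersion or power for endpoint 1, so there is no figure to reproduce. Its size figures are consistent: 44 × 100 = 4,400 enrolled, and 22 × 80 = 1,760 analysed per group.

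**Inputs from the SAP.** Two-sided 5% level and 95% intervals (section 3.1); 22 homes per group (section 2.3); "44 nursing homes with an average of 96 residents each" (section 2.1). Section 2.3 plans with 100 residents per home. Step 1 does not involve home size, so the difference is immaterial there.

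**Assumptions, not in the SAP.** Mean length of stay m from 3 to 12 days, with CV from 0 to 1.

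**Step 1: stays alone.** Let the number of stays be Poisson and let each stay last L days. The variance-to-mean ratio of total days is

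φ = E[L²]/E[L] = m(1+CV²).

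This is never below m. The planned model fixes φ = 1. Its interval is too narrow by √φ, and its actual two-sided error is 2·(1 − Φ(1.96/√φ)). At φ = 1 this returns 5.0%, as it should.

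| m (days) | CV | φ | √φ | false positives |
|---|---|---|---|---|
| 3 | 0 | 3.0 | 1.73 | 25.8% |
| 3 | 0.5 | 3.75 | 1.94 | 31.1% |
| 4 | 0.5 | 5.0 | 2.24 | 38.1% |
| 5 | 0.75 | 7.81 | 2.80 | 48.3% |
| 8 | 0 | 8.0 | 2.83 | 48.8% |
| 6 | 0.75 | 9.38 | 3.06 | 52.2% |
| 8 | 0.5 | 10.0 | 3.16 | 53.5% |
| 8 | 1 | 16.0 | 4.00 | 62.4% |
| 12 | 1 | 24.0 | 4.90 | 68.9% |

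Across the assumed range the factor runs from 1.73 to 4.90 and the error from 25.8% to 68.9%. A factor of 3 needs φ = 9, and an error of 50% needs φ = 8.44.

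**Step 2: the planned model under no effect.** Trials were simulated with 44 homes in 8 regions, about 96 residents per home, and group, baseline rate and region in the model. Further assumptions were 0.6 stays per resident-year, a correlation of 0.5 between the home effects at baseline and follow-up, and number of residents standing in for the bed-day offset. There were 1,500 runs per row. The last column scales the standard error by the Pearson dispersion and uses a t reference on the residual degrees of freedom: 44 − 10 = 34, the 10 being the intercept, group, baseline and 7 region terms.

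| m | CV | between-home log-SD | mean φ | √φ | plain Poisson error | scaled error |
|---|---|---|---|---|---|---|
| 3 | 0.5 | 0 | 3.80 | 1.95 | 31.1% | 4.8% |
| 4 | 0.5 | 0 | 5.03 | 2.24 | 37.3% | 4.5% |
| 5 | 0.75 | 0 | 7.77 | 2.79 | 49.1% | 5.1% |
| 8 | 0.75 | 0 | 12.4 | 3.52 | 59.9% | 4.9% |
| 3 | 0.5 | 0.2 | 9.47 | 3.08 | 52.5% | 5.4% |
| 5 | 0.75 | 0.2 | 17.5 | 4.18 | 64.9% | 4.5% |
| 8 | 0.75 | 0.2 | 27.5 | 5.24 | 73.5% | 6.5% |
| 8 | 0.75 | 0.3 | 45.7 | 6.76 | 77.3% | 5.5% |

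The rows without between-home variation agree with the formula in step 1. The other rows show how differences between homes add to the problem. Scaling brings the error to 4.5% to 6.5% in all eight rows. A separate simulation with 0.8 stays per resident-year and 600 runs per scenario gave 4% to 7% after the same correction.

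**The case against.** **The endpoint is exploratory.** This stands as a limit on severity: no confirmatory claim rests on the p-value. It does not make the interval valid, and the SAP still promises a 95% CI and a p-value.

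**The SAP has an overdispersion check.** It has one, for the primary endpoint. Section 5.4.3 would allow the same for endpoint 1, but optionally and outside the study report, so the published figure would remain uncorrected.

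**Poisson regression may be shorthand for a model with robust or scaled errors.** The text gives no sign of this. The resident-level models in section 5.1.3 and the Covid-19 model in section 5.4.2 name nursing-home random intercepts. Resident-level total hospital days (endpoint 14) have one; endpoint 1 does not.

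**The outcome is described as a number per 100 residents.** With about 96 residents per home, rescaling multiplies φ by about 100/96 = 1.04. It cures nothing.

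**The size rests on assumptions.** This stands. A reader might infer that intervals are always at least 3 times too narrow and that a null effect would look significant more often than not. The SAP does not support such minimums. They need m(1+CV²) of about 9 (8.44 for the 50% mark), and a constant 8-day stay falls short of both, at 2.83 times and 48.8%. Factors above 5 in the working come from between-home variation of assumed size, which is a separate source.

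**Other endpoints.** A reader might also extend the point to endpoints 2, 4 and 5 c–d. These count stays, deaths and resuscitation attempts, so the multi-day-stay argument does not reach them. Nor is a defect shown for the resident-level day and hour counts (14, 17, 19). Their nursing-home intercept absorbs most of the excess, and a small simulation gave 6% to 9% error from 80 runs per scenario, with a Monte Carlo standard error of √(0.05 × 0.95/80) = 2.4 points at 5%.

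**Conclusion.** The concern holds for endpoint 1. That the variance is understated follows from counting days rather than stays: φ is at least the mean length of stay, provided admissions vary at least as much as a Poisson count. How far it is understated depends on a length of stay that the SAP does not give. Over the assumed range in step 1, the nominal 5% test is invalid even at the most favourable end, where about one null trial in four would be declared significant. Because the endpoint is exploratory and not a key secondary, this is a correction that should be made rather than a threat to the trial's main conclusion.

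**What to change.** In SAP section 5.1.3, take endpoint 1 out of the plain Poisson group and specify as its main, reported analysis one of the following, keeping the offset and covariates:

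- a quasi-Poisson model with the standard error scaled by the Pearson dispersion and a t reference on the residual degrees of freedom; or
- a negative binomial model with small-sample robust standard errors.

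The first option is the one checked above; the second was not simulated here. The choice should be fixed in the text, not left to section 5.4.3.

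The cost is a sentence and a model option, with no change to design or data. The interval widens by √φ, which was 1.9 to 6.8 times in the simulated scenarios, so endpoint 1 will be visibly less precise. That precision was never in the data.

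### Exploratory NH-level endpoints 1, 2, 4, 5c and 5d: the Poisson model takes a rate per 100 residents as its outcome and also a bed-day offset, so home size is divided out twice

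*SAP*

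**What the plan says.** SAP section 5.1.3, under the NH-level heading, opens with "All secondary endpoints are count data". For endpoints 1, 2, 4, 5c and 5d it then specifies a Poisson regression "with the respective number per 100 residents per past 12 months' observation period (from t1 to t2) as dependent variable", with "number of occupied bed days as offset and the respective baseline rate and region of NHs as covariates". The effect is reported as an IRR with 95% CI and p-value, together with marginal estimates per arm.

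Section 1.2.2 defines the endpoints on the same scale: endpoint 1 is the "number of hospital days (long-term) per 100 residents per past 12 months", endpoint 4 the "number of residents who died in the hospital per 100 residents per past 12 months", and 5c and 5d fall under the "number of pre-specified unwanted invasive treatments per 100 residents measured". Endpoint 2, hospital stays, is also per 100 residents, and its definition says that occupied bed days are disregarded.

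The other models under the same heading are worded differently. Endpoints 5a, 5b, 6, 7, 8a and 9a are modelled "with the respective number as dependent variable, group (intervention vs. control) as independent variable, number of residents as offset". For 8b–d and 9b–e, "a Poisson Regression model is calculated with the respective number as dependent variable" and the number of ADs or POLST-Es is the offset. In these models the per-100 scale appears only in the marginal estimates.

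**The concern.** In a Poisson rate model the outcome is the count and the offset carries the denominator. Here the stated outcome has already been divided by residents, and the bed-day offset, which is close to proportional to residents, divides by size again. The fitted quantity is then events per resident per bed day, which is not the endpoint in section 1.2.2.

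Two things follow if the sentence is executed as written. A difference in home size between arms enters the IRR even when the intervention does nothing. The Poisson variance also treats every home as if it had 100 residents, whatever its real size, so the reported confidence interval and p-value do not reflect the true variability.

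Some imbalance in size is to be expected: 44 homes are randomised within centre and region (section 2.2), home size is not a stratification factor, and size varies enough for section 5.4.1 to plan a subgroup split at 100 residents.

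**Working it through.** The SAP gives no event rate, effect size or power for these endpoints, so there is no figure of its own to reproduce.

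**Inputs from the SAP.** 44 homes, 22 per arm, averaging 96 residents (sections 2.1 and 2.3); 8 regions; 1:1 allocation stratified by centre and region; region and baseline rate as covariates; two-sided 5% tests without multiplicity adjustment for secondary outcomes (section 3.1).

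**Assumed, not in the SAP.** Coefficient of variation (CV) of home size 0.2, 0.35 or 0.5; event rates per 100 resident-years as shown below; Poisson counts with no extra variation; no treatment effect.

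**Algebra, group term only.** Let home i in arm g have N_i residents, C_i events and 365·N_i bed days. As written, Y_i = 100·C_i/N_i with offset log(365·N_i). The Poisson score equations give each arm's fitted rate as ΣY/Σ(bed days). With true rate λ_g per resident this is 100·λ_g/(365·mean N_g), so

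IRR as written = (λ_1/λ_0) × (mean N_0/mean N_1).

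With raw counts each arm's rate is λ_g/365, and the IRR is λ_1/λ_0.

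**Example, no effect, λ = 0.06.** Control homes have 96 residents, intervention homes 96 × 1.1 = 105.6.
- Control: 6/(365 × 96) = 0.0001712
- Intervention: 6/(365 × 105.6) = 0.0001557
- Ratio: 0.909
- Raw counts: 0.06/365 in both arms, ratio 1.000

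**With region in the model**, and the size ratio the same in every region, the fitted null IRRs are:

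| Size ratio, intervention/control | 0.8 | 0.9 | 1.0 | 1.1 | 1.2 | 1.5 |
|---|---|---|---|---|---|---|
| As written | 1.250 | 1.111 | 1.000 | 0.909 | 0.833 | 0.667 |
| Raw count | 1.000 | 1.000 | 1.000 | 1.000 | 1.000 | 1.000 |

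Where size differed only between regions, the overall size ratio was 0.948 but the IRR with region was 1.000 (1.055 without region). It is therefore the within-region imbalance that passes through.

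**Size of chance imbalance.** The SD of the log size ratio is about CV × √(2/22) = 0.302 × CV. For CV 0.2 this is 0.060, and the 95% range is exp(±1.96 × 0.060) = 0.89 to 1.13. In simulation the ranges were about 0.89–1.13, 0.82–1.24 and 0.75–1.34 for the three CVs.

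**Simulated type I error** (1,500 trials per cell, stratified allocation, region and baseline rate in the model):

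| Assumed rate per 100 | CV 0.2 | CV 0.35 | CV 0.5 |
|---|---|---|---|
| 50 (order of a hospital-stay rate) | 28% | 45% | 60% |
| 6 (in-hospital deaths) | 9% | 16% | 26% |
| 2 (CPR attempts) | 6.5% | 10% | 17% |

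Raw counts with the bed-day offset gave 3.8% to 5.2% throughout. A second set of 1,000 trials per scenario gave 10%, 16% and 28% for deaths at 8 per 100, and 6%, 9% and 17% for CPR at 2 per 100.

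**Cross-check at 6 per 100.** As written, each arm contributes about 22 × 100 × 0.06 = 132 nominal events, so the model-based SE of the log IRR is about √(2/132) = 0.123. The simulated SD was 0.142, 0.176 and 0.218. The critical value 1.96 × 0.123 = 0.241 is then 1.70, 1.37 and 1.11 true SDs, which implies rejection rates of about 9%, 17% and 27%. This agrees with the table.

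**Direction.** The mean log IRR as written lay between −0.010 and 0.002 in every scenario. The slope of the log-IRR error on the log size ratio was −0.93 to −1.02, so the baseline-rate covariate does not remove the distortion.

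**The case against.** The strongest reply is that this is a drafting slip. The section says these endpoints are counts. Section 1.2.1 builds the per-100-per-year scale from bed days, so the sentence may only be naming the endpoint and then its one denominator. The same per-100 phrase recurs as the scale of the marginal estimates, and every neighbouring model is a count with one offset. This is plausible and may be what was meant. It does not settle the matter: no sentence replaces the rate by the raw number for these endpoints, and the clear wording next door makes the difference look intended to whoever programs it.

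The magnitudes are also conditional. The CVs and event rates are assumptions, and the type I errors arise only if the sentence is followed literally. The inverse-ratio relation does not depend on them.

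Three stronger readings are tempting and not supported. A reader might infer that any size imbalance passes fully into the IRR; the region covariate absorbs the part that lies between regions. A reader might infer a bias in favour of one arm; over repeated randomisations the log IRR is centred on zero, so the harm is a chance distortion in the one trial run, with too small a standard error. A reader might infer that the marginal rates are lost; they are distorted when standardised over both arms, but each arm's fitted values at its own offsets still sum to its observed values.

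**Conclusion.** The point holds: as written, the model for endpoints 1, 2, 4, 5c and 5d divides by home size twice and contradicts the rest of its own section. A within-region size ratio r between arms multiplies the IRR by about 1/r, for example 0.91 for r = 1.1. Type I error for deaths or CPR attempts is roughly 6% to 28% instead of 5%, given size CVs of 0.2 to 0.5, rates of 2 to 8 per 100 and Poisson counts.

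It would be wrong to infer that the trial's main conclusions are at risk. Section 5.1.3 calls the secondary analyses explorative, and the primary endpoint and the key secondary endpoints (9e, 10a ii, 10b ii) use other models. The sentence should be fixed, because these results will carry IRRs, intervals and p-values. The negative binomial check in section 5.2 is planned only for the primary endpoint and would not catch this.

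**What to change.** In section 5.1.3, NH level, replace the description of the outcome for endpoints 1, 2, 4, 5c and 5d as follows:

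- Dependent variable, all five endpoints: the raw number of events (or days) in the home from t1 to t2.
- Offset for 1, 4, 5c and 5d: log(occupied bed days), and no other denominator.
- Offset for 2: reconcile it with the definition in section 1.2.2, which sets bed days aside; log(number of residents) would fit that definition.
- Use the scale per 100 residents per year only to express the marginal estimates. For the bed-day models this is the prediction at 365 × 100 = 36,500 bed days.

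The cost is a sentence or two in the SAP. No new data are needed: homes already report the numbers, bed days and residents. The change should be made before the analyst knows the size distribution by arm, so that the choice between the two readings cannot depend on it.
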